**Table 10: Analysis Windows for Body Weight** 

Visit Label	Targeted DBTP Study Day	Targeted SBTP Study Day	Analysis Window in Study Days	SBTP Analysis Window in Study Days
Screening	< Day 1	N/A	Measurement obtained prior to 1st study trt, and not defined as baseline visit	N/A
Baseline	Day 1	N/A	Measurement obtained closest to 1st study trt	N/A
Week 1	8	N/A	Day 2 to 15	N/A
Week 3	22	N/A	16 to 29	N/A
Week 5	36	N/A	30 to 39	N/A
Week 6	43	N/A	40 to 50	N/A
Week 8	57	N/A	51 to 64	N/A
Week 10	71	N/A	65 to 78	N/A
Week 12	85	N/A	82 to SB Day 1	N/A
Week 14	N/A	SB Day 15	N/A	SB Day 2 to 22
Week 16	N/A	29	N/A	23 to 36
Week 18	N/A	43	N/A	37 to 50
Week 20	N/A	57	N/A	51 to 64
Week 22	N/A	71	N/A	65 to 78
Week 24	N/A	85	N/A	79 to 92
FU- W5	Last study trt admin day + 35 days	Last study trt	Last study trt admin day +15 days TO last study trt admin day + 49 days	
FU-W9	Last study trt admin day + 63 days	Last study trt admin day + 50 days TO last study trt admin day + 77 days		
FU-W13	Last study trt admin day + 91 days	Last study trt admin day + 78 days TO last study trt admin day + 105 days		
FU-W17	Last study trt admin day + 119 days	Last study trt admin day + 106 days TO last study trt admin day + 126 days		

Table 11: Efficacy Analysis Windows for Fasting Triglycerides and Fasting Glucose

Visit Label	Targeted DBTP Study Day	Targeted SBTP Study Day	Analysis Window in Study Days	SBTP Analysis Window in Study Days
Screenin g	< Day 1	N/A	Measurement obtained prior to 1st study trt, and not defined as baseline visit	N/A
Baseline	Day 1	N/A	Measurement obtained closest to 1st study trt while remaining prior to 1st study trt admin	N/A
Week 2	15	N/A	Day 2 to 22	N/A
Week 4	29	N/A	23 to 36	N/A
Week 6	43	N/A	37 to 50	N/A
Week 8	57	N/A	51 to 64	N/A
Week 10	71	N/A	65 to 74	N/A
Week 11	78	N/A	75 to 81	N/A
Week 12	85	N/A	82 to SB Day 1	N/A
Week 14	N/A	SB Day 15	N/A	SB Day 2 to 22
Week 16	N/A	29	N/A	23 to 36
Week 18	N/A	43	N/A	37 to 50
Week 20	N/A	57	N/A	51 to 64
Week 22	N/A	71	N/A	65 to 74
Week 23	N/A	78	N/A	75 to 81
Week 24	N/A	85	N/A	82 to 92
FU- W5	Last study trt admin day + 35 days		Last study trt admin day +15 days TO last study trt admir day + 49 days	
FU- W9	Last study trt admin day + 63 days		Last study trt admin day + 50 d day + 77	
FU- W13	Last study trt admin day + 91 days		Last study trt admin day + 78 d day + 105	
FU- W17	Last study trt admin day + 119 days		Last study trt admin day + 106 days TO last study trt admin day + 126 days	

Table 12: Efficacy Analysis Windows for HbA1c

Visit Label	Targeted Study DBTP Day	Targeted SBTP Study Day	Analysis Window in DBTP Study Days	Analysis Window in SBTP Study Days
Screening	< Day 1	N/A	Measurement obtained prior to 1st study trt, and not defined as baseline visit	N/A
Baseline	Day 1	N/A	Measurement obtained closest to 1st study trt while remaining prior to 1st study trt admin	N/A
Week 4	29	N/A	Day 2 to 36	N/A
Week 6	43	N/A	37 to 57	N/A
Week 10	71	N/A	58 to 78	N/A
Week 12	85	NA	79 to SB Day 1	N/A
Week 16	N/A	SB Day 29	N/A	SB Day 2 to 36
Week 18	N/A	43	N/A	37 to 57
Week 22	N/A	71	N/A	58 to 78
Week 24	N/A	85	N/A	79 to 92
FU- W5	Last study trt admin day + 35 days			+15 days TO last study trt y + 49 days
FU- W9	Last study trt admin day + 63 days			+ 50 days TO last study trt y + 77 days
FU- W13	Last study trt admin day + 91 days			+ 78 days TO last study trt + 105 days
FU- W17	Last study trt adm	in day + 119 days		+ 106 days TO last study trt

**Table 13: Efficacy Analysis Windows for Daily Lipodystrophy Hunger Questionnaire** 

Visit Label	Analysis Window in DBTP Study Days	Analysis Window in SBTP Study Days	
Baseline	Day -27 to Day 1 while remaining prior to 1st DB study trt admin	N/A	
Week 4	Day 2 to 29	N/A	
Week 8	30 to 57	N/A	
Week 12	58 to SB Day 1 while remaining prior to 1st SB study trt admin or to last study trt admin day + 7 days if not entering SBTP	N/A	
Week 16	N/A	SB Day 2 to 29	
Week 20	N/A	30 to 57	
Week 24	N/A	58 to Last study trt admin day + 7 days	
FU- W5	Last study trt admin day +8 days TO last study trt admin day + 35 days		
FU- W9	Last study trt admin day + 36 days TO last study trt admin day + 63 days		
FU- W13	Last study trt admin day + 64 days TO last study trt admin day + 91 days		
FU- W17	Last study trt admin day + 92 days T	O last study trt admin day + 119 days	

Table 14: Efficacy Analysis Windows for DXA, MRI, NMR Lipid, and Bioimpedance

Visit Label	Targeted Study DBTP Day	Targeted SBTP Study Day	Analysis Window in DBTP Study Days	Analysis Window in SBTP Study Days
Baseline	Day 1	N/A	Measurement obtained closest to 1st study trt while remaining prior to 1st study trt admin	N/A
Week 12	85	NA	Day 43 to SB Day 1 or to last DB trt admin day + 28 days if not entering SBTP	N/A
Week 24	N/A	SB Day 85	N/A	SB Day 43 to last SB trt admin day + 28 days
FU- W17	Last study trt admin	day + 119 days	Last study trt admin day + 69 day + 13.	•

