8.4.2. Study Drug Discontinuation

Patients who permanently discontinue from study drug before entering TP1 (day 1) will be contacted to assess any adverse events (AEs) but will not be asked to return for the remaining study visits.

Patients who permanently discontinue from study drug after entering TP1 should be encouraged to remain in the study. Those who agree and do not withdraw from the study will be asked to return to the clinic for all remaining study visits per the visit schedule.

Patients who permanently discontinue from study drug and who opt to withdraw from the study will be asked to complete study assessments, per Section 9.1.3.

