# 5.7. Analyses of Efficacy Variables

For statistics where international and conventional units do not impact the results (eg, means and least square (LS) means for percent changes from baseline, statistical testing for both percent and absolute changes from baseline, rates of patients below a threshold), derivations will be calculated and statistical models will be run using conventional units. For other statistics (eg, descriptive statistics at baseline and over time, absolute changes from baseline), derivations will be presented in both international and conventional units.

All efficacy assessment values obtained during the study (scheduled or unscheduled) can be used to provide a value for the efficacy endpoints as appropriate.

All efficacy measurements will be assigned to Efficacy Analysis Windows defined in Appendix 10.2, with the intent to provide an assessment for week 1 to 24 time points. For all visits post-baseline, the value used for the analyses at a given time point (eg, at week 12) is the value obtained within the corresponding efficacy analysis window. If multiple values exist for an analysis window, the value obtained closest to the targeted time of the window will be used as appropriate. Unless otherwise specified, the baseline value is defined as the last available measurement before the first double-blind study treatment administration. For patients randomized and not treated, the baseline value is defined as the last available value prior to the date of randomization.

Statistical analyses for the primary efficacy endpoints will be completed during the first step efficacy analysis (Section 7). Remaining descriptive efficacy analyses will be completed during the second step analyses.

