#### 5.7.2.1. Continuous Endpoints Anticipated to have a Normal Distribution

Continuous secondary variables defined in Section 4.7.2 and Section 4.7.3 anticipated to have a normal distribution (including HbA1c, fasting glucose, and liver fat) will be analyzed using a similar MMRM model as described for the primary endpoint in HbA1c.

Daily lipodystrophy hunger questionnaire (DLHQ) will be descriptively summarized from baseline to week 12 and again from baseline to week 24. Mean changes in monthly averaged DLHQ scores (±SE) will be plotted across visits by treatment group; a spaghetti plot will be provided for individual patient data across visits by treatment group. Monthly averaging windows of the DLHQ scores are defined in the Efficacy Analysis Windows for Daily Lipodystrophy Questionnaire (See Appendix 10.2). If a participant reported less than 10 scores

Protocol: R4461-PLD-20100

within a monthly averaging window for a DLHQ item, the averaged score will be assigned a missing value.

The statistical estimates, comparisons, and descriptive statistics for these secondary efficacy variables are summarized in Table 3, Table 4, Table 5, and Table 6.

Table 3. Summary of Statistical Estimates and Comparisons in Normally-distributed Secondary Endpoints

Endpoint	Cohort for Modeling	Analysis Method / Estimates	Comparisons
• Absolute change in HbA1c from baseline to week 12.	• Separately for Cohort B and Cohort A+B	MMRM / Least-squares (LS) means with their corresponding standard errors and 95% confidence intervals.  Note: Strata level = HbA1c>7.0%.  Note: Post baseline visits to include in the model are weeks 4, 6, 10, and 12.	REGN4461 versus Placebo with nominal p- value.
• Change in fasting glucose from baseline to week 12.	• Separately for Cohort A, Cohort B, and Cohort A+B	MMRM / Least-squares (LS) means with their corresponding standard errors and 95% confidence intervals.  Note: Strata level = HbA1c>7.0%.  Note: Post baseline visits to include in the model are weeks 2, 4, 6, 8, 10, 11, and 12.	REGN4461 versus Placebo with nominal p- value.
• Percent change in liver fat (MRI-PDFF) from baseline to week 12	• Separately for Cohort A, Cohort B, and Cohort A+B	MMRM / Least-squares (LS) means with their corresponding standard errors and 95% confidence intervals.  Note: patient subgroup = baseline MRI-PDFF ≥8.5%  Note: Post baseline visit at week 12.	REGN4461 versus Placebo with nominal p- value.

Protocol: R4461-PLD-20100

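### SAP Table 13 ends the hunger windows 7 days after last dose, so patients who stop drug early but keep the diary cannot have a week-12 (or week-24) hunger value

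*SAP*

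**What the plan says.** Change in the DLHQ from baseline to weeks 12 and 24 is a secondary endpoint (Protocol 4.2; SAP 4.7.2). SAP 5.7.2.1 averages the daily scores over monthly windows, and the DLHQ "will be descriptively summarized from baseline to week 12 and again from baseline to week 24".

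Table 13 in SAP 10.2 sets the windows. Week 4 is Days 2 to 29 and week 8 is Days 30 to 57. For a patient who enters TP2, week 12 is "58 to SB Day 1 while remaining prior to 1st SB study trt admin". For a patient who does not, a second clause sets the end of the window instead: "or to last study trt admin day + 7 days if not entering SBTP". Week 24 runs from SB Day 58 to 7 days after last dose. The first follow-up window, FU-W5, is "Last study trt admin day +8 days TO last study trt admin day + 35 days", and later follow-up windows continue to last dose + 119 days.

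SAP 5.7.2.1 adds a minimum count. The condition is "If a participant reported less than 10 scores". The consequence, which is stated separately for each item, is "within a monthly averaging window for a DLHQ item, the averaged score will be assigned a missing value".

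On follow-up, Protocol 8.4.2 says: "Patients who permanently discontinue from study drug after entering TP1 should be encouraged to remain in the study". Protocol 6.1 lists the daily hunger measure among the off-drug follow-up assessments, and the diary row of the Schedule of Events runs to week 40. On populations, SAP 3.1.1 analyses the FAS as randomised and SAP 5.7.2 places the secondary efficacy variables in the FAS.

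**The concern.** The window end depends on when the patient stopped drug, which happens after randomisation and may be related to the outcome: a patient may stop for lack of benefit or for intolerance. Combined with the 10-score minimum, an early stop leaves no week-12 hunger value however complete the diary is. The scores that would have supplied it are relabelled as follow-up.

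Hunger is a stated secondary objective. DLHQ summaries and plots are among the outputs that SAP 1.2.4 keeps after early termination. Because the DLHQ is only summarised descriptively, no model or imputation stands in for the missing averages. The week-12 summary would then describe those who stayed on drug beyond about week 8, plus anyone who entered TP2, under a label that says FAS as randomised.

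**Working it through.** **Inputs.** Week-12 window start: Day 58. Window end for a patient not entering SBTP: last dose day L + 7 (both SAP Table 13). Minimum scores: 10 (SAP 5.7.2.1). Scores per item per day: 1 (SAP 4.12.1). Scheduled TP1 doses: Day 1 IV, then 11 weekly SC doses on Days 8 to 78 (Protocol 6.1 and Table 2). Visit window: ±3 days.

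**Full-course patient first.** Last scheduled TP1 dose is Day 78, so the window ends on Day 78 + 7 = 85 and holds 85 − 58 + 1 = 28 days. Week 4 (29 − 2 + 1) and week 8 (57 − 30 + 1) also hold 28 days. The rule gives a normal monthly window only when every dose was taken.

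**Early stopper.** Most scores possible = max(0, (L + 7) − 58 + 1) = max(0, L − 50). An average needs L − 50 ≥ 10, so L ≥ 60.

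| Last dose day | Window end | Most scores possible | Week-12 average |
|---|---|---|---|
| 50 or earlier | 57 or earlier | 0 | missing |
| 57 | 64 | 7 | missing |
| 59 | 66 | 9 | missing |
| 60 | 67 | 10 | only if no day is missed |
| 64 | 71 | 14 | possible |
| 71 | 78 | 21 | possible |
| 78 | 85 | 28 | possible |

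On the nominal schedule the last affected dose day is Day 57, the ninth of 12 administrations. With the ±3-day window, a week-8 dose given on Day 58 or 59 is affected too.

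**Week 24.** SB Day = study day − 84 on the nominal schedule, so the last TP2 dose (Day 162) is SB Day 78, and 78 + 7 = SB Day 85. The same formula applies in SB days: a last dose on SB Day 59 or earlier gives no week-24 value.

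**Where the scores go.**
- L = 57: FU-W5 is Days 65 to 92, so 85 − 65 + 1 = 21 days of the week-12 month become follow-up.
- L = 29: FU-W5 is Days 37 to 64 and FU-W9 is Days 65 to 92, so Days 58–64 and 65–85 go to those two windows.
- L = 22: FU-W5 is Days 30 to 57, which is exactly week 8. The week-4 and week-8 windows are not cut at last dose, so the same scores carry two labels.

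**Would the diary exist?** Protocol 9.1.3 runs off-drug follow-up to 16 weeks (112 days) after last dose. Even for a last dose on Day 1 that is Day 113, past Day 85. A diary kept through off-drug follow-up therefore covers Days 58 to 85 for any TP1 stopper who stays in the study.

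**Other endpoints.** The week-12 windows for fasting TG (from Day 82) and HbA1c (from Day 79) have no last-dose cut-off (SAP Tables 11 and 12), and MRI allows last dose + 28 days (Table 14). A patient with last dose on Day 57 who is assessed on Day 85 can supply week-12 TG, HbA1c and MRI values (57 + 28 = 85), but not hunger.

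**Size per patient.** One of 10 planned per arm per cohort is 10%; one of 20 per arm in the combined cohorts is 5%.

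**The case against.** The best defence is that Table 13 is an on-treatment convention. Protocol 9.1.3 moves patients who stop drug but stay into off-drug follow-up, so calling their later scores follow-up matches that structure. SAP Table 15 also closes the double-blind period at last dose + 14 days for patients who do not go on. SAP 5.7 is permissive rather than binding: "All efficacy assessment values obtained during the study (scheduled or unscheduled) can be used to provide a value" is qualified as applying where appropriate, and values are then assigned to the Appendix 10.2 windows. SAP 3.5 says clinical outcome assessments are analysed as treated. All of this is in the text, and no estimand is stated.

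It does not rescue the rule. Neither document states an on-treatment strategy for hunger. The cut-offs after last dose are 7, 14 and 28 days in Tables 13, 15 and 14, and there is none for TG or HbA1c. Weeks 4 and 8 are not cut at all. SAP 3.5 conflicts with SAP 5.7.2 and 5.12, which use the FAS, and assigning patients as treated would not justify a last-dose cut-off.

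Two stronger readings are tempting.
- A reader might infer that early stoppers leave the hunger analysis altogether. They do not: SAP 3.5 keeps anyone with a baseline and at least one week of later scores, and the week-4, week-8 and follow-up averages remain. A patient who misses late TP1 doses but enters TP2 is unaffected at week 12, and one who withdraws has no later diary under any window.
- A reader might size the bias by assuming hunger returns fully to baseline on stopping. With 10 per arm and k stoppers, 1/(1 − k/10) − 1 gives 11%, 25% and 43% for k = 1, 2 and 3. That is a worst case only. The documents give no hunger effect. Protocol 3.2.1 describes weight regain after stopping as complete only by about 16 weeks, and a Day-57 stopper is at most 28 days off drug by Day 85. The sum also ignores stoppers on placebo.

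**Conclusion.** The point stands in a limited form. A patient who stops drug permanently with an actual last dose on Day 59 or earlier (scheduled Day 57 or earlier), stays in the study and keeps the diary cannot have a week-12 hunger value. The parallel rule removes the week-24 value for patients who stop by SB Day 59. Overlapping labels for early stoppers are a separate defect of the same table.

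The consequence is selective missingness in a descriptive secondary summary and its plot. Protocol 11.1 plans no formal hypothesis test, and TP2 has no placebo arm, so the week-24 part affects no placebo comparison. The total size is unknown because no dropout rate is given. The 10% per patient assumes the planned 10 per arm per cohort; SAP 1.2.4 records limited enrolment, so the share may be larger. The conclusion assumes that patients off drug go on completing the diary, which the schedule provides for but Protocol 8.4.2 and 9.1.3 describe inconsistently.

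**What to change.** In SAP Table 13:
- Week 12: Day 58 to SB Day 1, before the first single-blind dose, for patients entering SBTP; otherwise Day 58 to Day 85.
- Week 24: SB Day 58 to SB Day 85, whether or not dosing stopped.
- State that scheduled-week windows take precedence and that follow-up labels apply only to scores that are both after Day 85 (or SB Day 85) and after last dose + 7 days, so that no score has two labels.
- Flag off-drug scores in the listing and spaghetti plot. If an on-treatment view is wanted, show that average alongside.

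Reconcile Protocol 8.4.2 with 9.1.3 on follow-up after stopping drug, and SAP 3.5 (as treated) with SAP 5.7.2 and 5.12 (FAS).

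The cost is table wording and programming, with no new data. For a last dose on Day 57 the available week-12 scores rise from 7 to 28; a full-course patient on the nominal schedule is unchanged. There are two downsides. Some week-12 and week-24 averages will include off-drug days, which the flag shows. Some early follow-up windows will also shrink: for last dose Day 57, FU-W5 keeps only Days 86–92, which is 7 scores and below the minimum. A patient who never receives a single-blind dose has no SB Day 1 and so has no week-24 window under either wording.

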#### **Table 15: Double-blind treatment period – Period Windows**

For those measurements that are collected over time (eg, IV and SC exposure), analyses performed within the 12-week double-blinded treatment period (DBTP) windows will use the following definitions to bin observations. Observations will be binned based on the start date of the measurement.

• The DBTP is defined as from the starting time of the first DBTP study drug administration to the day of the last DBTP study drug administration + 14 days for those patients not proceeding into the single-blinded treatment period (SBTP). For those patients proceeding into the SBTP, the DBTP ends at the starting time of the first SBTP study drug administration.

•

#### **Table 16: Single-blind treatment period – Period Windows**

For those measurements that are collected over time (eg, IV and SC exposure), analyses performed within the 12-week single-blinded treatment period (SBTP) windows will use the following definitions to bin observations. Observations will be binned based on the start date of the measurement.

• The SBTP is defined from the time of the first SBTP study drug administration to the day of the last SBTP study drug administration + 14 days.

•

#### Table 17: Double-blind treatment-emergent adverse event period – Period Windows

• The double-blind treatment-emergent adverse event (TEAE) period is defined from the starting time of the first dose of double-blind study treatment administration to the day of the last dose of double-blind study treatment administration + 112 days (16 weeks) for those patients not proceeding into SBTP, or up to the starting time of the first dose of SBTP study treatment administration for those patients proceeding into the SBTP.

•

#### Table 18: Single-blind treatment-emergent adverse event period – Period Windows

- The single-blind treatment-emergent adverse event (TEAE) period is defined from the starting time of the first single-blind study treatment administration to the day of the last single-blind study treatment administration + 112 days (16 weeks).
- •
- •

Protocol: R4461-PLD-20100

### 10.3. List of AESIs with Data Sources and Definitions of SMQ/CMQ

Table 19: Summary of AESIs and the Methods of Data Collections and Derivations

AESI	Using an e-CRF specific tick box on AE page	Using Standard MedDRA Query (SMQ)/company MedDRA Query (CMQ) or Laboratory data criteria
Hypoglycemia	Yes	Blood glucose <54 mg/dL
New onset diabetes mellitus (NODM)	Yes	For patients with no diabetes at baseline:
		• Two values of fasting (≥8 hr) plasma glucose ≥126 mg/dL (7.0 mmol) during treatment period
		OR
		• Two values of HbA1c ≥6.5% (48 mmol/mol) during treatment period
		Note: Patients who meet either of these criteria during the PBO run- in period will be considered to have diabetes at baseline.
Hyperglycemia requiring treatment	Yes	HbA1c ≥10.5% AND increase in HbA1c of ≥1.5% from baseline value OR b. Fasting glucose ≥250 mg/dL on 2 occasions AND increase in fasting glucose >50 mg/dL above baseline
Development of new or worsening of autoimmune disease	Yes	N/A
Moderate and severe Hypersensitivity reactions	Yes	CMQ 'Hypersensitivity, which is defined as Hypersensitivity SMQ (narrow) excluding the following PTs:

Protocol: R4461-PLD-20100

		0	Injection site
			dermatitis,
		0	Injection site eczema,
			Injection site
			hypersensitivity,
		0	Injections site rash,
		_	•
		0	injection site reaction,
		0	Injection site recall
			reaction,
		0	Injection site urticaria,
		0	Injection site vasculitis
Moderate and severe	Yes	N/A	
infusion reactions	105	14/11	
iniusion reactions			

^ dedicated CRF for ISR captures event PT and associated symptoms

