10. SAFETY EVALUATION AND REPORTING

10.1. Recording and Reporting Adverse Events

10.1.1. General Guidelines

The investigator must promptly record all AEs occurring during the study data collection, from the time of signing the informed consent form (ICF) to the end of the study (see Section 11.4.5.1). Medical conditions that existed or were diagnosed prior to the signing of the Informed Consent will be recorded as part of medical history. Abnormal laboratory values and vital signs observed at the time of Informed Consent should also be recorded as medical history. Any subsequent worsening (ie, any clinically significant change in frequency and/or intensity) of a pre-existing condition that is temporally associated with the use of the study drug should also be recorded as an AE.

At each visit, the investigator will determine whether any AEs have occurred by evaluating the patient. Adverse events may be directly observed, reported spontaneously by the patient, or by questioning the patient at each study visit. Patients should be questioned in a general way, without asking about the occurrence of any specific symptoms. The Investigator must assess all AEs to determine seriousness, severity, and causality, in accordance with the definitions in Section 10.2. The Investigator's assessment must be clearly documented in the site's source documentation with the Investigator's signature. The Investigator should follow up on serious adverse events (SAEs) (and AESIs) until they have resolved or are considered clinically stable; AEs should be followed until they are resolved or last study visit, whichever comes first.

Always report the diagnosis as the AE or SAE term. When a diagnosis is unavailable, report the primary sign or symptom as the AE or SAE term with additional details included in the narrative until the diagnosis becomes available. If the signs and symptoms are distinct and do not suggest a common diagnosis, report them as individual entries of AE or SAE.

Laboratory results, vital signs, and other diagnostic results or findings should be appraised by the Investigator to determine their clinical significance. Isolated abnormal laboratory results, vital sign findings, or other diagnostic findings (ie, not part of a reported diagnosis) should be reported as AEs if they are symptomatic, lead to study drug discontinuation, dose reduction, require corrective treatment, or constitute an AE in the investigator's clinical judgment.

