# 4.8.1.2. Adverse Events of Special Interest

Adverse events of special interest (AESI) are AEs (serious or non-serious) required to be monitored, documented, and managed in a pre-specified manner. AESIs will be recorded on the adverse event e-CRF using dedicated tick boxes, and/or identified using standard MedDRA queries (SMQ), company MedDRA queries (CMQ), MedDRA terms, and/or applicable laboratory assessments. Appendix 10.3 contains the definitions used to identify AESIs:

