#### The AESIs include:

- Hypoglycemia, defined as blood glucose <54 mg/dL (eCRF, lab data)
- New onset diabetes mellitus (NODM) (eCRF, lab data)
- For patients with no diabetes at baseline, NODM is defined using the following lab parameters:
  - a. Two values of fasting ( $\geq 8$  hours) plasma glucose  $\geq 126$  mg/dL (7.0 mmol) during the treatment period

OR

- b. Two values of HbA1c ≥6.5% (48 mmol/mol) during the treatment period
- Hyperglycemia requiring treatment (eCRF, lab data), defined using the following lab parameter:
  - a. HbA1c ≥10.5% AND at the same visit an increase in HbA1c of ≥1.5% from baseline value

OR

- b. Fasting glucose ≥250 mg/dL on 2 occasions including symptoms consistent with hyperglycemia AND increase in fasting glucose >50 mg/dL above baseline
- Development of new or worsening of autoimmune disease (eCRF)
- Moderate or severe hypersensitivity reactions (CMQ, eCRF)
- Moderate or severe infusion reactions (eCRF)

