#### **5.8.2.** Analysis of Adverse Events of Special Interest

Treatment-emergent adverse events of special interest (AESI), as listed in Section 4.8.1.2, will be presented by SOC and PT as applicable. AESI are defined by SMQ, CMQ, lab data, and/or dedicated e-CRF are summarized by frequency (%) as described in Appendix 10.3.

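### SAP Table 19 drops the symptom condition from the glucose limb of the AESI 'hyperglycemia requiring treatment', so a symptom-free patient could be counted as a case

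*SAP*

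**What the plan says.** SAP 4.8.1.2 introduces the event as "Hyperglycemia requiring treatment (eCRF, lab data), defined using the following lab parameter" and gives its glucose limb as "Fasting glucose ≥250 mg/dL on 2 occasions including symptoms consistent with hyperglycemia AND increase in fasting glucose >50 mg/dL above baseline". Protocol 10.1.3 (events for expedited reporting) and Protocol 8.10.2 (new hyperglycemia needing rescue insulin, to be reported as an AESI) state the same limb, also with symptoms.

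SAP Appendix 10.3, Table 19 gives that limb as "Fasting glucose ≥250 mg/dL on 2 occasions AND increase in fasting glucose >50 mg/dL above baseline". The sentence is complete, with no gap or redaction.

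On which text governs, SAP 4.8.1.2 states: "Appendix 10.3 contains the definitions used to identify AESIs". It says AESIs are recorded by e-CRF tick boxes "and/or identified using standard MedDRA queries (SMQ), company MedDRA queries (CMQ), MedDRA terms, and/or applicable laboratory assessments". SAP 5.8.2 then refers to both places. Its first sentence is "Treatment-emergent adverse events of special interest (AESI), as listed in Section 4.8.1.2, will be presented by SOC and PT as applicable"; its second is "AESI are defined by SMQ, CMQ, lab data, and/or dedicated e-CRF are summarized by frequency (%) as described in Appendix 10.3".

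**The concern.** A programmer who builds the AESI frequency row from Table 19 and one who builds it from SAP 4.8.1.2 would apply different rules to the same patients, and the SAP sends them to both. Under the Table 19 rule, a patient with no symptoms who crosses the glucose thresholds could be reported as having an event that the protocol defines as symptomatic.

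At stake is whether one row of a safety table means what the protocol says it means. If the mismatch is found only after unblinding, someone must choose between two rules that may give different counts by arm.

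**Working it through.** No sample-size, power or event-rate figure is involved, so the check is a comparison of texts followed by a short logical argument.

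**Step 1. The four statements of the glucose limb.**

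| Place | Two fasting values ≥250 mg/dL | Rise >50 mg/dL | Symptoms required |
|---|---|---|---|
| Protocol 10.1.3 | yes | yes | yes |
| Protocol 8.10.2 | yes | yes | yes |
| SAP 4.8.1.2 | yes | yes | yes |
| SAP Table 19 | yes | yes | no |

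SAP 1.2.4 lists departures from the protocol's statistical section and does not mention this one.

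**Step 2. Where the rules disagree.** Let H = HbA1c limb met, G = both glucose thresholds met, S = symptoms present.

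- Protocol 10.1.3 and SAP 4.8.1.2: H or (G and S).
- Table 19: H or G.

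With S known, the two differ only when H is no, G is yes and S is no. There Table 19 counts the patient and the protocol rule does not. No patient is a case under the protocol rule and missed by Table 19, so the error can go only upward. If symptoms were simply not recorded, the true status cannot be determined: Table 19 may over-count, or a rule needing recorded symptoms may under-count.

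The HbA1c limb raises no separate issue. SAP 4.8.1.2 adds that both parts must be met at the same visit and Table 19 does not. At patient level this changes nothing: if any value reaches 10.5% and any value is at least 1.5 points above baseline, the highest value does both.

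**Step 3. Which outputs are exposed.** The SOC and PT presentation in the first sentence of SAP 5.8.2 needs a coded term. A laboratory hit with no reported AE has none, so it cannot enter that table. It could enter only the frequency summary that the second sentence takes from Appendix 10.3.

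**Step 4. An upper bound on the excess.** The hyperglycemia PCSV in SAP Table 20 uses the same two thresholds but needs only one occasion (SAP 5.8, general common rules: at least 1 PCSV in the TEAE period). Let M be a patient's highest fasting glucose in that period. If two values are ≥250 mg/dL, then M ≥250 mg/dL. If any value is >50 mg/dL above baseline, so is M. Every patient who meets the Table 19 glucose limb therefore also meets the PCSV. Hence the number over-counted cannot exceed the number with the hyperglycemia PCSV. This assumes the same baseline and period for both, and that M lies outside the laboratory's normal range, as Table 20 also requires.

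**The case against.** The strongest defence is that Table 19 was never meant to restate the whole definition. The cell sits in a column headed for query or laboratory criteria, beside a tick-box column marked yes. Symptoms are not laboratory data, so the column may hold only the part that can be programmed, with the full definition left to SAP 4.8.1.2. SAP 4.8.1.2 also describes AESIs as adverse events, Protocol 10.1.3 has laboratory-based AESIs reported once the investigator confirms the value, and Protocol 8.10.2 gives treated symptomatic cases a reporting route.

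Much of this stands. The omission is probably a drafting slip, and the SOC and PT table is protected. It does not remove the conflict, because SAP 4.8.1.2 keeps symptoms inside wording it calls a lab parameter itself, the tick-box and laboratory sources are joined by and/or, and no text requires a laboratory hit to be confirmed by symptoms or by a tick box. Confirming a glucose value is not confirming symptoms.

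A reader might go further and infer that the sponsor deliberately widened the event, or that the reported AESI rate will be materially inflated. The documents support neither. No change is declared, three of the four texts keep the symptom condition, and nothing says how many patients would meet the thresholds without symptoms.

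**Conclusion.** The inconsistency is real and minor. Table 19, as written, is a broader rule than the protocol's. Where symptom status is known, it can only over-count the AESI relative to Protocol 10.1.3 and SAP 4.8.1.2. The documents give no basis for sizing the excess: it may be zero, and it cannot exceed the hyperglycemia PCSV count under the assumptions above. Counting how many logical patterns differ, or what share of an arm one patient represents, would not be an effect size.

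The effect is limited to one row of a descriptive safety summary. Efficacy results are untouched. The early-termination changes in SAP 1.2.4 reduce the efficacy analyses and drop the step analyses, but they do not remove the AESI summary. The conclusion assumes that the programmed row follows Table 19 as written; if the programming used SAP 4.8.1.2 instead, the count would be right and only the document would need correcting.

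**What to change.** Before database lock, make the glucose limb in Table 19 identical to SAP 4.8.1.2: "Fasting glucose ≥250 mg/dL on 2 occasions including symptoms consistent with hyperglycemia AND increase in fasting glucose >50 mg/dL above baseline". Add one sentence saying that laboratory-only hits, meaning thresholds met with symptoms absent or not recorded, are not pooled with the AESI count. This costs one table cell and one sentence, with no protocol change and no new data collection.

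There is a small downside. The documents do not show that hyperglycemia symptoms are elicited systematically. For adverse events, Protocol 10.1.1 says "Patients should be questioned in a general way, without asking about the occurrence of any specific symptoms"; the scheduled monitoring in Protocol 9.2.3.6 asks about hypoglycemia symptoms; and Protocol 8.7 blinds investigators to fasting glucose up to week 24. Some true cases may therefore go unconfirmed. This should not be overstated, since Protocol 8.10.2 requires treated symptomatic hyperglycemia to be reported as an AESI and home glucometer readings are reviewed where applicable.

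Unconfirmed cases stay visible in the PCSV summaries and patient listings under SAP 5.8.4, where repeated high values can be seen. A separately labelled supportive row for the two-occasion laboratory criterion is optional. It would isolate the repeated cases, which the PCSV count does not do because one occasion is enough, but the listings already show most of what it would add.
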